2.2.1. Descriptive Analyses

Standard descriptive statistics will be used to summarize the demographics and baseline clinical characteristics of the participants (**Table 1**), and also to summarize primary and key secondary outcomes

related to OXT vs. PBO (**Table 2**). We will describe the retention during the study and adherence to OXT or PBO. Waterfall plots will be provided to display the change in body weight for each participant, stratified by the treatment (OXT vs. PBO). Additionally, spaghetti plots of the body weight measured at each visit will be made to inform the trajectory of body weight change over time during each treatment block. Similar plots will be produced for other outcomes of interest.

2.2.2. Adverse Events (AE)

Treatment-related AEs in each treatment period (OXT vs. PBO) will be summarized and reported as count (and %) in tables (**Table 3**). In this Table, we will include any AE that is at least possibly related to study drug, and either occurs in at least 2 participants (with any CTCAE grade for severity) and/or occurs in at least 1 participant (with CTCAE Grade 2 or higher). McNemar test will be performed to compare the prevalence of the AEs of interest between OXT and PBO. We will describe changes in ECG parameters and in sodium levels/DDAVP use, since cardiovascular and fluid balance considerations are special AEs of interest.

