 - 18) Parents/guardians or subjects who, in the opinion of the Investigator, may be non-compliant with study schedules or procedures.

If vital signs and/or laboratory tests initially indicate ineligibility, select metrics may be repeated, and if eligibility is then demonstrated on repeat, subject will be enrolled. Subjects that do not meet all of the enrollment criteria may not be enrolled. Any violations of these criteria must be reported in accordance with IRB Policies and Procedures.

Number Of Subjects	N = 150 enrolled participants (Children’s Hospital of Philadelphia); because parents are engaged in research, we anticipate 150 participant-parent/legal guardian dyads, N = 20 participants with complete data. Adult participants, living independently, may enroll individually.
Study Duration	Each subject’s participation will last approximately 7 months. The entire study is expected to last 3 years.
Study Phases Screening Study Treatment	Participants will undergo a telephone screening and then, within 4 weeks, complete an in-person screening visit to determine eligibility. Then, within 4 weeks they will be randomized and begin 8 weeks of treatment with either OXT or placebo. After a 4-week “washout,” participants will cross-over to 8 weeks of treatment with the other condition (i.e., placebo or OXT).

Efficacy Evaluations	Efficacy will be evaluated for each subject by the difference in body weight over the 8 weeks while on OXT versus the 8 weeks while taking placebo.
Pharmacokinetic Evaluations	During one of the CHPS-monitored doses of each of OXT and placebo, serial peripheral blood measurements of OXT will be made.
Safety Evaluations	i) Heart rate and blood pressure during CHPS-monitored doses of OXT/placebo; ii) EKG; iii) serum sodium; iv) any need to adjust synthetic vasopressin therapy for diabetes insipidus; v) safety monitoring uniform report form (SMURF) assessments (including potential symptoms such as fluid retention, nausea/vomiting, nasal irritation)
Statistical And Analytic Plan	The within-subject effect of OXT (versus placebo) on weight change over 8 weeks will be assessed using linear mixed-effects model with the outcome being the difference of the post-treatment weight between two periods (treatment vs. placebo), adjusted for the difference of the baseline weight between the two periods as covariate.

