1.0. Definition of the Endpoints

1.1. The primary endpoint will be the change in body weight over 8 weeks during OXT versus placebo treatment.

1.2. Secondary endpoints will include the following:

- Cognitive restraint (stop-signal task) after monitored dose of OXT versus placebo
- Calories consumed (as a percentage of calories offered) during a test meal after a monitored dose of OXT versus after a monitored dose of placebo
- The change in arm circumference, over 8 weeks during OXT versus placebo
- The change in waist circumference, over 8 weeks during OXT versus placebo
- The change in hyperphagia (Hyperphagia Questionnaire), hunger, disinhibition of eating, cognitive restraint (Eating Inventory), mental/emotional health and quality of life (Neuro-QOL), family function (FAD-GRS) over 8 weeks during OXT versus placebo
- Fat mass, lean mass, and % body fat (DXA) at the conclusion of 8 weeks OXT versus 8 weeks of placebo
- Resting energy expenditure (REE) at the conclusion of 8 weeks OXT versus 8 weeks of placebo
- Respiratory quotient (RQ) at the conclusion of 8 weeks OXT versus 8 weeks of placebo
- Usual energy intake (calories/day via self-reported 3-day diet record) at the conclusion of 8 weeks OXT versus 8 weeks of placebo
- Change in self-reported physical activity (via BMDCS-PA questionnaire) during 8 weeks of OXT versus 8 weeks of placebo
- OXT pulse profiling after exogenous OXT vs placebo
- Safety and tolerability of OXT based on AEs

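### SAP 2.2.2 limits its one named AE table to events at least possibly related to study drug, and no supplied section plans an AE summary regardless of attribution

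*SAP*

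**What the plan says.** SAP 1.2 lists among the secondary endpoints "Safety and tolerability of OXT based on AEs". The protocol synopsis has a matching secondary objective. Neither is restricted by causality.

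The analysis is in SAP 2.2.2. It opens with "Treatment-related AEs in each treatment period (OXT vs. PBO) will be summarized and reported as count (and %) in tables", pointing to Table 3, and then sets the entry rule: "In this Table, we will include any AE that is at least possibly related to study drug". An AE must also occur either in at least two participants at any CTCAE grade or in at least one participant at Grade 2 or higher.

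The test is described separately: "McNemar test will be performed to compare the prevalence of the AEs of interest between OXT and PBO". The SAP does not list these AEs. It then says that changes in ECG parameters, sodium levels and DDAVP use will be described, "since cardiovascular and fluid balance considerations are special AEs of interest", with no relatedness condition.

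SAP 2.2.1 adds "We will describe the retention during the study and adherence to OXT or PBO". It does not link stopping to AEs.

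**The concern.** The endpoint concerns AEs, while the planned table concerns AEs that someone judged at least possibly caused by study drug. In a randomized, double-blind, placebo-controlled cross-over, the placebo block already supplies the background rate, so the treatment comparison does not need case-by-case attribution. Attribution may also be hard here. That is an inference: every participant has a brain tumor history and at least one further endocrinopathy, so many events will have a plausible competing cause.

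At stake is whether a reader could check for an imbalance that nobody attributed to the drug. Under the supplied plan, an AE judged unrelated, whatever its grade or frequency, appears in no named AE output by treatment. The protocol's Safety Evaluations collect symptoms on a uniform report form (fluid retention, nausea or vomiting, and nasal irritation are its examples) with no relatedness condition, so unfiltered information appears to be available.

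**Working it through.** **Step 1. Does any planned output show AEs regardless of attribution?** The claim is about scope, and the plan gives no figure to reproduce. These are all the supplied places that bear on safety:

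| Place | Relatedness limit? | All-causality AE summary? |
|---|---|---|
| Protocol synopsis, secondary objective | No | States an aim only |
| Protocol synopsis, Safety Evaluations | No | Data collection only |
| Protocol synopsis, monitoring plan (DSMB) | Not stated | No tabulation described |
| SAP 1.2, safety endpoint | No | Defines the endpoint only |
| SAP 2.2.1, Table 2 (key secondary outcomes) | Not stated | AEs not named |
| SAP 2.2.1, retention and adherence | No | No link to AEs |
| SAP 2.2.2, Table 3 | Yes | No |
| SAP 2.2.2, McNemar test | Unclear | Its AEs are not defined |
| SAP 2.2.2, ECG, sodium, DDAVP | No | Parameters and drug use only |

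No row is an all-causality AE summary.

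**Step 2. What does Table 3 drop?** Its rule is: (at least possibly related) AND (at least 2 participants at any grade OR at least 1 participant at Grade 2 or higher). If the first condition fails, the AE is out whatever the second says. A related Grade 1 AE seen in one participant is also out, but that is an ordinary display choice and not the point here.

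**Step 3. Illustration of how much could be hidden.** The documents give neither the share r of AEs judged at least possibly related nor the number dosed, n. I assume n = 20 or 10. The protocol synopsis gives 20 as participants with complete data, but SAP 2.4 says the recruitment goal was not reached. I assume r from 25% to 90%, an AE of Grade 2 or higher (so the frequency cut-off does not act), a 10% risk on OXT, at most one event per person per block, independence between people, and attribution unrelated to true cause.

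P(occurs on OXT, but no OXT case is judged related) = (1 − 0.1r)^n − 0.9^n.

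For example, n = 20 and r = 0.5 give 0.95^20 − 0.9^20 = 0.3585 − 0.1216 = 0.237.

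If instead one related case in either block admits the AE term with all its cases, and placebo risk is also 10%, multiply by (1 − 0.1r)^n, the chance of no related case on placebo. The example becomes 0.237 × 0.3585 = 0.085.

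| r | n = 20, per event | n = 20, per term | n = 10, per event | n = 10, per term |
|---|---|---|---|---|
| 25% | 0.481 | 0.290 | 0.428 | 0.332 |
| 50% | 0.237 | 0.085 | 0.250 | 0.150 |
| 75% | 0.089 | 0.019 | 0.110 | 0.050 |
| 90% | 0.030 | 0.005 | 0.041 | 0.016 |

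The range is too wide to size the problem for this trial.

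**Step 4. The filter can also help.** Take assumed all-cause risks of 40% on OXT and 10% on placebo, a 30-point difference. If a random half is judged related, the table shows 20% against 5%, or 15 points. If attribution is perfect, the drug-caused risk d solves 1 − 0.9(1 − d) = 0.40, so d = 1/3, and the table shows 33% against 0%. Which case is nearer the truth is unknown, so both views are needed.

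**The case against.** The strongest reply is that the risks the sponsor singles out are already handled without the filter. ECG, sodium and DDAVP changes are described whatever the attribution, retention is described, and a DSMB is planned. That stands and narrows the gap: what goes unshown by treatment is chiefly AEs outside the cardiovascular and fluid-balance areas that were judged unrelated.

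Second, a threshold of at least possible relatedness is inclusive. If nearly all events pass it, little is lost, as the 90% row shows. This also stands, since nothing in the documents fixes the share.

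Third, the SAP describes itself as supporting the findings in the main text, so Table 3 may be a manuscript display, and only a protocol synopsis is supplied. Fuller AE reporting rules may exist elsewhere. The point is therefore confined to the supplied documents.

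A reader might go further and infer that the whole AE comparison, test included, rests on attribution. The text does not support that. The filter is written for the table, while McNemar applies to AEs of interest, which are undefined. The next sentence uses a similar phrase for cardiovascular and fluid-balance events with no relatedness condition. The test may be filtered or not.

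A reader might also infer that the filter makes OXT look safer. The documents do not show this either. The trial is double-blind and Step 4 shows that the filter can sharpen a contrast as well as shrink it.

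**Conclusion.** The point holds as a cheap improvement, not as an error that invalidates the plan. The one named AE table is narrower than the endpoint it serves, and no supplied section plans a summary of all AEs, serious AEs or AEs leading to discontinuation regardless of attribution. This rests on the wording alone and needs none of the assumed rates.

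No direction or size of bias is established. The illustrative probabilities, from under 1% to 48%, depend on assumed attribution shares, event risks and numbers dosed. Confidence is medium, because a full protocol may contain AE reporting rules that the synopsis omits.

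**What to change.** In SAP 2.2.2:

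- Add an AE table regardless of causality, by treatment received, with everyone dosed in that block as the denominator. Include serious AEs and AEs leading to discontinuation.
- Keep the at-least-possibly-related events as a second column of that table.
- Name the AEs of interest. Run McNemar on them regardless of attribution and give the related-only result beside it.

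The cost is SAP wording and a longer table. It should need no new data, since Table 3 is itself a selection from AEs already recorded. The downside is that background events will also appear and may dilute a drug effect that accurate attribution would isolate, which is why the related-only column and test stay.

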2.3. Additional Sensitivity Analyses

We will test the effect of sequentially adding age, gender, as well as the adherence to treatment to the primary model as sensitivity analyses to understand the extent to which these may influence the main result. Adherence is defined in two ways that capture different dimensions of likely effect: first, the average % of doses consumed as compared to prescribed during each treatment block, and second, the % of days during each block with complete adherence. In exploratory analyses, we will also test the extent to which hypothalamic damage (as reflected by the presence or absence of diabetes insipidus, and by centralized MRI-based assessment of hypothalamic damage) impacts response to treatment.

2.4. Power Calculations

We will perform power calculation based on our current sample size and observed standard deviation (SD) of the within-subject difference in the weight loss between OXT and PBO. Specifically, we will calculate the detectable effect size (and 95% CI) of the weight loss difference between OXT and PBO to reach 80% power at significance level of 0.05. We then compare this effect size with the observed effect size. Since we did not reach the original recruitment goal due to the COVID19 pandemic and new considerations regarding risk for QTc interval prolongation, we will do similar calculations and comparisons assuming the originally planned sample size.
